### **7.3. Body Weight, Height, BMI and Vital Signs**

Descriptive statistics will be provided by renal function group for vital signs (including body temperature, pulse rate, respiratory rate, systolic and diastolic blood pressure) as specified below:

- Predose value
- Values at each postdose time point
- Change from predose at each postdose time point

Predose and postdose values will be defined as described in Section 3.7.1. Change from predose to a postdose visit will be defined as the postdose value minus the predose value.

In the case of multiple values in an analysis window, data will be selected for analysis as described in Section 3.7.3. No inferential statistical testing is planned.

A by-subject listing of vital signs will be provided by subject ID number and time point in chronological order. Body weight, height, and BMI will be included in the vital signs listing, if space permits, otherwise they will be provided separately.

### **7.4. Concomitant Medications**

Medications collected at screening and during the study will be coded using the current version of the World Health Organization (WHO) Drug dictionary.

A summary of concomitant medications will not be provided.

All concomitant medications (other than per-protocol study drugs) will be provided in a by-subject listing sorted by subject ID number and administration date in chronological order.

### **7.5. Electrocardiogram Results**

#### **7.5.1. Investigator Electrocardiogram Assessment**

A shift table of the investigator's assessment of ECG results at each scheduled visit compared with predose values will be presented by renal function group using the following categories:

normal; abnormal, not clinically significant; abnormal, clinically significant; or missing. The number and percentage of subjects in each cross-classification group of the shift table will be presented. Subjects with a missing value at predose or postdose will not be included in the denominator for percentage calculation. No formal statistical testing is planned.

A by-subject listing for ECG assessment results will be provided by subject ID number and time point in chronological order.

#### **7.6. Other Safety Measures**

A by-subject listing of subject pregnancies during the study will be provided by subject ID number. No additional safety measures are specified in the protocol.

Although not necessarily related to safety, a by-subject listing of all comments received during the study on the comments form will be provided by subject ID number, and form for which the comment applies.

#### **7.7. Changes From Protocol-Specified Safety Analyses**

There are no changes from the protocol-specified safety analyses.

## 8. PHARMACOKINETIC EVALUATION/ANALYSIS

### 8.1. Estimation of Pharmacokinetic Parameters

Pharmacokinetic parameters will be estimated using Phoenix WinNonlin® software using standard noncompartmental methods. The linear/log trapezoidal rule will be used in conjunction with the appropriate noncompartmental model, with input values for dose level, dosing time, plasma concentration, and corresponding real-time values, based on drug dosing times whenever possible.

All predose sample times before time-zero will be converted to zero.

For area under the curve (AUC), samples below the limit of quantitation of the bioanalytical assays occurring prior to the achievement of the first quantifiable concentration will be assigned a concentration value of zero to prevent overestimation of the initial AUC. Samples that are BLQ at all other time points will be treated as missing data in WinNonlin. The nominal time point for a dosing interval ( $\tau$ ) may be used to permit direct calculation of AUC over specific time intervals. The appropriateness of this approach will be assessed by the PK scientist on a profile-by-profile basis.

Pharmacokinetic parameters such as  $AUC_{inf}$ ,  $\lambda_z$ , and  $t_{1/2}$  are dependent on an accurate estimation of the terminal elimination phase of the drug. The appropriateness of calculating these parameters will be evaluated upon inspection of PK data on a profile-by-profile basis by the PK scientist.

Renal clearance ( $CL_r$ ) will be derived by dividing amount excreted in urine ( $A_e$ ) through  $t$  hours postdose (eg.  $t = 120$  hrs) by  $AUC_{0-t}$  (eg.  $AUC_{0-120}$ ). The determination of  $t$  will be based on the availability of data and assessed by the PK scientist. Fraction excreted unchanged through  $t$  hours postdose ( $fe_{0-t}$ ) will be derived by dividing amount excreted in urine ( $A_e$ ,  $\mu g$ ) through the last urine sampling timepoint over the dose (mg) administered. A conversion factor may be deployed to adjust the differences in reported units before deriving  $CL_r$  and  $fe_{0-t}$ . For example, if the units of  $A_e$ ,  $AUC_{0-t}$ , and the dose are  $\mu g$ ,  $h \cdot ng/mL$ , and mg, respectively, the following equations will be utilized:

$$CL_r \text{ (mL/min)} = (A_e \times 1000) / (60 \times AUC_{0-t});$$

$$fe_{0-t} = 100 \times A_e / (\text{Dose} \times 1000).$$

#### 8.1.1. Pharmacokinetic Parameters

Pharmacokinetic parameters for GS-9876 will be generated for all subjects for whom parameters can be derived.

The parameters presented in [Table 8-1](#) and [Table 8-2](#) will be used to evaluate the PK objectives of the study. The primary parameters are plasma PK parameters  $AUC_{last}$ ,  $AUC_{inf}$ , and  $C_{max}$  of

GS-9876. The PK parameters to be estimated in this study are listed and defined in PK Abbreviations section.

**Table 8-1. Plasma Pharmacokinetic Parameters**

Analyte	Parameters
GS-9876	AUC last , AUC inf , %AUC exp , C max , T max , C last , T last , λ z , CL/F, V z /F, and t 1/2 , as applicable

**Table 8-2. Urine Pharmacokinetic Parameters**

Analyte	Parameters
GS-9876	CL r , A e , and f e , as applicable

## 8.2. Statistical Analysis Methods

### 8.2.1. General considerations

Individual subject concentration data and individual subject PK parameters including percentage of protein binding for GS-9876 will be listed and summarized using descriptive statistics by renal function group. Summary statistics (numbers of subjects, mean, SD, coefficient of variation, median, minimum, maximum, Q1, and Q3) will be presented for both individual subject concentration data by time point and individual subject PK parameters by renal function group. Moreover, the geometric mean, 95% CI, and the mean and SD of the natural log-transformed values will be presented for individual subject PK parameter data.

Individual concentration data listings and summaries will include all subjects with concentration data. The sample size for each time point will be based on the number of subjects with nonmissing concentration data at that time point. The number of subjects with concentration BLQ will be presented for each time point. For summary statistics, BLQ values will be treated as zero at predose and one-half of the LLOQ for postdose time points.

Individual PK parameter data listings and summaries will include all subjects for whom PK parameter(s) can be derived. The sample size for each PK parameter will be based on the number of subjects with nonmissing data for that PK parameter.

In addition to the renal function categorization based on CLcr throughout this study, MDRD-based eGFR will be used for subject categorization in PK analysis. Subjects from all cohorts will be pooled and regrouped according to their MDRD-based eGFR values as follows:

- Normal renal function if eGFR (rounding to the nearest integer) is  $\geq 90$  mL/min/1.73m^2
- Mild impairment if eGFR (rounding to the nearest integer) is 60-89 mL/min/1.73m^2
- Moderate impairment if eGFR (rounding to the nearest integer) is 30-59 mL/min/1.73m^2

- Severe impairment if eGFR (rounding to the nearest integer) is 15-29 mL/min/1.73m^2
- End stage renal impairment if eGFR (rounding to the nearest integer) is  $\leq 14$  mL/min/1.73m^2

The following tables will be provided for GS-9876 by two sets of categorization (CLcr and MDRD-based eGFR) of renal function group:

- Individual subject concentration data and summary statistics
- Individual subject plasma PK parameters and summary statistics

The following figures will be provided for GS-9876 by two sets of categorization of renal function group:

- Mean ( $\pm$  SD) concentration data versus time (on linear and semilogarithmic scales)
- Median (Q1, Q3) concentration data versus time (on linear and semilogarithmic scales)

A figure of individual subject concentration data versus time (on linear and semilogarithmic scales) will be provided.

Individual, mean, and median postdose concentration values that are  $\leq$  LLOQ will not be displayed in the figures and remaining points will be connected.

The following listings will be provided:

- Pharmacokinetic sampling details by subject, including differences in scheduled and actual draw times, and sample age
- Individual data on determination of plasma half-life and corresponding regression correlation coefficient

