1.5. Risk/Benefit Assessment for the Study

While there is no direct benefit for the subject participating in the renal impairment study of GS-9876, the risks are considered to be minimal for the following reasons:

GS-9876 has been in a battery of nonclinical animal studies, and no renal toxicity was identified.

GS-9876 has been tested in humans as a single ascending dose over a dose range of 2 to 50 mg (GS-US-379-1372) and as a multiple ascending dose over a dose range of 15 to 50 mg (GS-US-379-1900) and no evidence of nephrotoxicity has been observed. In general GS-9876 was well tolerated at all dose levels. The planned single dose of 20 mg of GS-9876 is well below the highest dose given in the healthy volunteers and is expected to be tolerated well.

As discussed in Section 1.3, the disposition of GS-9876 is primarily via hepatic metabolism and elimination with minimal excretion expected in urine and the impact on renal impairment on GS-9876 PK is expected to be limited. Subjects in this study will receive a single 20 mg dose of GS-9876, which is expected to provide a margin of 2.8-fold to the NOAEL exposure in the 39-week Cynomolgus monkey toxicology study.

Evidence of deterioration in kidney function in humans can readily be detected and monitored using routine laboratory tests. For this study, frequent assessments of kidney function will be performed from the collection of both blood and urine samples. While subjects with renal impairment will be enrolled, the risk of further kidney injury in these subjects should be minimized by this close renal monitoring. Further, this study will enroll subjects with moderate renal impairment (Cohort 1) with a screening estimated creatinine clearance (CL_{cr}) of 30-59 mL/min first. Data from these subjects will be compared to matched subjects with normal renal function ($CL_{cr} \geq 90$ mL/min). Subjects with severe renal impairment (Cohort 2; CL_{cr} 15-29 mL/min) will only be evaluated if supported by safety and/or PK data from Cohort 1.

There are several potential causes of nephropathy in patients with chronic autoimmune diseases: primary autoimmune attack on the kidney, secondary renal amyloidosis, drug-related renal disease due to necessary drugs used to treat the primary autoimmune disease. Kidney disease and

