4.2.3. For Healthy Matched Controlled Subjects (Subjects with Normal Renal Function)

Healthy matched control subject must also meet the following additional inclusion criteria to be eligible for participation in this study:

- 1) Must, in the opinion of the investigator, be in good health based upon medical history and physical examination, including vital signs.
- 2) Have a creatinine clearance (CL_{cr}) ≥ 90 mL/min (using the Cockcroft-Gault method {[Cockcroft et al 1976](#)}) based on serum creatinine and actual body weight as measured at screening, ie,

Male:
$$\frac{(140 - \text{Age [years]}) \times (\text{Weight [kg]})}{72 \times (\text{Serum Creatinine [mg/dL]})} = CL_{cr} \text{ (mL/min)}$$

Female:
$$\frac{(140 - \text{Age [years]}) \times (\text{Weight [kg]}) \times 0.85}{72 \times (\text{Serum Creatinine [mg/dL]})} = CL_{cr} \text{ (mL/min)}$$

- 3) Match in age (± 10 years), gender, and body mass index ($\pm 20\%$, ≥ 18 kg/m² and ≤ 36 kg/m²).

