### 1.3. Study Design

Study GS-US-379-1932 is an open-label, parallel-group, adaptive, single-dose, multi-center Phase 1 study to evaluate the PK of GS-9876 in subjects with impaired renal function.

This study will target enrolling 20 to 60 subjects using an adaptive design that includes up to 3 enrolled cohorts of subjects with renal impairment and matched healthy controls. Based on safety and PK results from subjects with moderate renal impairment (Cohort 1), subjects with severe renal impairment (Cohort 2) and/or mild renal impairment (Cohort 3) will be enrolled as follows:

[figure not shown]
- Cohort 1 (Moderate Renal Impairment): Up to 20 subjects (10 per group, moderate renal impairment and matched healthy controls) for 8 evaluable subjects per group.
- Adaptive Cohort 2 (Severe Renal Impairment): Up to 20 subjects (10 subjects with severe renal impairment and up to 10 matched healthy control subjects if none of the healthy subjects from a previous cohort is an appropriate match for a severe impairment subject) for 8 evaluable subjects per group.

- Adaptive Cohort 3 (Mild Renal Impairment): Up to 20 subjects (10 subjects with mild renal impairment and up to 10 matched healthy control subjects if none of the healthy subjects from a previous cohort is an appropriate match for a mild impairment subject) for 8 evaluable subjects per group.

Adaptive Cohorts 2 and/or 3 will be enrolled as determined by safety and/or PK data in Cohort 1. Specifically, Cohort 2 (Severe Renal Impairment) will be evaluated if supported by safety and/or PK data from Cohort 1 (Moderate Renal Impairment). Cohort 3 (Mild Renal Impairment) will be evaluated if supported by safety and if substantial changes ( $\geq 2$ -fold mean difference from matched controls) in the exposure of GS-9876 is observed in subjects with moderate renal impairment in Cohort 1. Cohorts 2 and 3 may not be enrolled or may be enrolled sequentially or in parallel, as governed by safety and PK data in Cohort 1. Each control subject may be matched to multiple renal impaired subjects across different cohorts and can be matched to only 1 renal impaired subject within a cohort.

An overview of the study design is shown in [Figure 1-1](#).

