**Figure 1-1. Study Design**

The categorization of renal impairment is based on creatinine clearance (CLCr) using the Cockcroft-Gault formula from the screening visit. Specifically, a subject will be considered as having

[figure not shown]
- Mild impairment if CLcr (rounding to the nearest integer) is 60-89 mL/min
- Moderate impairment if CLcr (rounding to the nearest integer) is 30-59 mL/min
- Severe impairment if CLcr (rounding to the nearest integer) is 15-29 mL/min

A subject with CLcr (rounding to the nearest integer) higher than or equal to 90 mL/min is categorized as having normal renal function.

Following screening and Day -1 procedures, eligible subjects will be confined to the study center beginning Day -1 until the completion of assessments on Day 6. Subjects will return 14 ( $\pm$ 1) days after last dose for an in-clinic follow up visit (ie, Day 15).

The study schema is shown in [Figure 1-2](#).

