### **8.2.2. Statistical Methodology**

The statistical comparisons of the natural log-transformed PK parameters for GS-9876 between renal impaired subjects and healthy controls will be performed. All subjects with available data for the PK parameter under evaluation will be included in the modeling.

Consistent with using two sets of renal function categorization in PK summaries, two corresponding sets of comparisons will be performed. Details of these comparisons are shown in [Table 8-3](#). To ensure the appropriateness of applications of statistical testing, the comparisons will only be implemented when there are at least 3 subjects in both test and reference groups. The ratio of geometric least squares means (GLSMs) for the PK parameter in comparison between the test and reference groups and the 90% CI for the ratio will be provided.

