**Table 8-3. Statistical Comparisons for Pharmacokinetic Analysis of Normal and Impaired Renal Function**

Renal Function Categorization	Parameter	Comparison	
		Test Group	Reference Group
Creatinine Clearance (rounding to the nearest integer)	AUC inf , AUC last , C max	Mild Impairment CLcr 60-89 mL/min	Normal CLcr ≥ 90 mL/min
	AUC inf , AUC last , C max	Moderate Impairment CLcr 30-59 mL/min	Normal CLcr ≥ 90 mL/min
	AUC inf , AUC last , C max	Severe Impairment CLcr 15-29 mL/min	Normal CLcr ≥ 90 mL/min
MDRD-based eGFR (rounding to the nearest integer)	AUC inf , AUC last , C max	Mild Impairment eGFR 60-89 mL/min/1.73m 	Normal eGFR ≥ 90 mL/min/1.73m 
	AUC inf , AUC last , C max	Moderate Impairment eGFR 30-59 mL/min/1.73m 	Normal eGFR ≥ 90 mL/min/1.73m 
	AUC inf , AUC last , C max	Severe Impairment eGFR 15-29 mL/min/1.73m 	Normal eGFR ≥ 90 mL/min/1.73m 
	AUC inf , AUC last , C max	End Stage Impairment eGFR ≤ 14 mL/min/1.73m 	Normal eGFR ≥ 90 mL/min/1.73m 

For each PK parameter in comparison, a parametric (normal theory) analysis of variance (ANOVA) model will be fitted to the natural log-transformed values of PK parameter under evaluation. The statistical model will include renal function group as a fixed effect.

The following SAS PROC MIXED code will provide the group comparison analysis between the renal function groups and the 90% CI calculations for natural log-transformed PK parameters.

```
proc mixed;
  class renalgrp subjid;
  model lnest = renalgrp / ddfm=kr;
  repeated / group = renalgrp;
  lsmeans renalgrp / e diff cl alpha = 0.1;
  estimate 'Impaired versus Normal' treat 1 -1 / cl alpha = 0.10;
  ods output Estimates = LS_Diffs LSMeans = LS_Means CovParms = MSE;
run;
```

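### Without a mild cohort, does the MDRD eGFR Mild-versus-Normal ratio mislead because it mostly compares enrolled controls with each other?

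*SAP*

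**What the plan says.** Enrolment uses Cockcroft-Gault creatinine clearance with actual body weight. For controls, SAP 1.3 states: "A subject with CLcr (rounding to the nearest integer) higher than or equal to 90 mL/min is categorized as having normal renal function". Protocol 4.2.3 adds the matching rule: "Match in age (± 10 years), gender, and body mass index".

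For the PK analysis, SAP 8.2.1 introduces a second categorization by MDRD eGFR with the same numerical cut-points: "Subjects from all cohorts will be pooled and regrouped according to their MDRD-based eGFR values as follows". The protocol synopsis already lists these eGFR categories and says selected results will be analysed by them as well.

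Table 8-3, titled "Statistical Comparisons for Pharmacokinetic Analysis of Normal and Impaired Renal Function", has one set of rows for each measure. One eGFR row has the test group "Mild Impairment eGFR 60-89" mL/min/1.73m² against eGFR of at least 90. SAP 8.2.2 puts one condition on every row: "the comparisons will only be implemented when there are at least 3 subjects in both test and reference groups".

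Whether subjects are enrolled as mildly impaired depends on Cohort 1. SAP 1.3 says "Cohort 3 (Mild Renal Impairment) will be evaluated if supported by safety and if substantial changes" of at least 2-fold are seen there. Protocol 1.5 anticipates that "the impact on renal impairment on GS-9876 PK is expected to be limited".

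**The concern.** The two equations do not measure the same thing. Cockcroft-Gault rises with body weight and is not indexed to body surface area. MDRD has no weight term and is expressed per 1.73 m². A heavier or older control can therefore be normal on the first and mild on the second.

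If the protocol's expectation is right, Cohort 3 stays closed. The subjects enrolled as impaired then have CLcr of 15-59 mL/min, and few of them reach eGFR 60. Controls are the main remaining source of the eGFR Mild group, and the 3-per-group rule does not look at how a subject was enrolled.

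The fear is false reassurance. A ratio near 1 in a row called Mild Impairment could be read as evidence about patients with kidney disease when few or none contributed to it.

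**Working it through.** **1. The plan's own figure.** SAP 1.4 gives 8 per group, SD 0.35 on the log scale, true ratio 1 and limits 50-200% (±ln 2 = ±0.693). The standard error is 0.35 × √(2/8) = 0.175 on 14 df. Exact two one-sided tests power is 0.966 (0.934 with 7 per group), so the stated probability of over 95% is reproduced. It is not in dispute.

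**2. Can a control move?** The formulas are in Protocol 4.2.3 and SAP 5.2. Take a man of 60, 85 kg, serum creatinine 1.0 mg/dL.
- CLcr = (140 − 60) × 85 / (72 × 1.0) = 94.4: normal.
- eGFR = 175 × 1.0^−1.154 × 60^−0.203 = 76.2: mild (92.4 with the 1.212 factor).

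**3. Which way is movement likelier?** Take a man of 65 without the 1.212 factor, so 175 × 65^−0.203 = 75.0.
- eGFR falls below 89.5 when creatinine exceeds (89.5/75.0)^(−1/1.154) = 0.858. A control with CLcr 90 becomes eGFR Mild above 90 × 72 × 0.858/75 = 74 kg. With CLcr 110 the weight is 91 kg.
- eGFR reaches 59.5 when creatinine is below (59.5/75.0)^(−1/1.154) = 1.222. A moderate subject with CLcr 59 becomes eGFR Mild only below 59 × 72 × 1.222/75 = 69 kg. With CLcr 45 the weight is 53 kg.
- Severe subjects do not get there. A woman of 75 with BMI 18, height 1.63 m and CLcr 29 has creatinine 1.27 and eGFR 41 (50 with the factor).

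**4. How often?** The documents give eligibility limits but no distributions, so these inputs are assumptions: mean age 50-65, mean BMI 23-30, half female, control male median creatinine 0.80-1.00 mg/dL, 0-30% African American, and moderate CLcr uniform on 30-59. Cohort 1 only, 8 + 8, 162 scenarios:

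| Quantity | Range | Middle scenario |
|---|---|---|
| Controls with eGFR 60-89 | 6-70% | 33-35% |
| Row run (at least 3 and 3) | 10-81% | 57-61% |
| Mean control share of Mild, if run | 30-99% | 91% |

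Controls averaged over half of the Mild group in 154 of the 162 scenarios. That counts chosen scenarios and is not a probability. The share is sensitive to the moderate group. With moderate CLcr at 45-59, mean age 65, mean BMI 26.5, control creatinine 0.80 and 30% African American, it falls to about 51%, and controls are the majority in 45% of runs.

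**5. What could the row show?** Suppose exposure followed enrolled disease status with a 1.5-fold effect. This effect is assumed, and it lies below the 2-fold trigger, so Cohort 3 would stay closed. The expected Mild ratio is 1.5^(1 − control share): 1.5^0.095 = 1.04 in the middle scenario and 1.5^0.696 = 1.33 at the lowest control share. The CLcr Moderate row in the same table would be centred on 1.5. Its noncentrality is ln 1.5/0.175 = 2.32, so its 90% CI lies wholly above 1 in about 71% of trials. If exposure follows eGFR itself, the Mild row is simply right.

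**6. How reassuring could it look?** Splitting 8 controls 3 v 5 or 4 v 4, with SD 0.35 and true ratio 1, puts the 90% CI inside 50-200% in only 49% or 56% of cases, against 97% for the planned 8 v 8.

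**7. What would remedies buy?**
- Withholding the ratio when half or more of the Mild group are controls would, in the middle scenario, suppress it in 57-60% of trials and keep it in 0.6%. That in effect deletes the row.
- A regression on continuous eGFR rests on log-linearity. If the truth were a 1.5-fold step below eGFR 60, a quadratic term would be significant in only 4-10% of trials with 16 subjects.
- Printing enrolled group beside the eGFR rows changes no estimate.

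**The case for a change.** The strongest case for a change is about presentation. The title of Table 8-3 speaks of impaired renal function, and SAP 8.2.2 describes all its comparisons as impaired subjects against healthy controls. A Mild group made up mainly of people recruited as healthy does not fit that description, and nothing at the row says so. The situation arises when the protocol's own expectation of a small renal effect holds. A count of enrolled group by eGFR group would cost almost nothing.

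Much of this stands. The composition is likely at mean BMI of about 25 and above, and more so if Cohort 2 brings in further controls. The 3-per-group rule does not prevent it.

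It does not show a fault in the analysis. A second categorization is useful only if it may disagree with the first. Treating Cockcroft-Gault status as the true status inside the MDRD analysis would defeat its purpose. Nor is the movement hidden. SAP 8.2.1 requires individual-subject plasma PK parameter tables under both categorizations, SAP 5.2 summarizes eGFR by CLcr group, and SAP 4.1 lists each subject's renal function group. A reader can see who moved. Enrolled counts beside the eGFR rows would be a courtesy of layout in the study report and need no change to the plan.

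**Conclusion.** No change follows. Without Cohort 3, the eGFR Mild group may consist largely of subjects enrolled as CLcr-normal controls. The mean control share is about 50% to 99% in the scenarios checked at mean BMI of about 26 or more, and lower in some lighter, older samples. These figures rest on assumed age, BMI, creatinine, race and moderate-CLcr distributions, which the documents do not give. If Cohort 3 opens, the point largely falls away.

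The composition is a foreseeable result of a prespecified second grouping, and the row states its eGFR range. Harm needs a chain of conditions: Cohort 3 closed, at least 3 subjects in each group, a control majority, a real effect that follows enrolled status and not eGFR, and a reader who prefers this row to the CLcr rows beside it. The opening of Cohort 3, the sample size and the CLcr comparisons do not use the row. The remedies either remove a planned estimate by an arbitrary threshold, add an assumption the data can hardly test, or repeat what the planned tables already show.
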